### 9.3.1. Additional Therapy

A patient should not receive additional therapeutic treatment for glioblastoma during the study period.

### 9.3.2. Additional Anti-Cancer Treatment and Radiotherapy

Patients should not receive additional therapeutic anti-cancer treatment until after PD has been documented on study and End of Treatment study assessments have been completed. If a patient requires additional anti-cancer treatment, study treatment will be discontinued and the patient will enter the Post-Treatment Period and followed every 8 weeks by phone call.

### 9.3.3. Interaction of Tesevatinib with Other Medications

Cytochrome P4503A4 is the major metabolic pathway of tesevatinib in humans. This suggests the potential for other drugs to significantly affect the biotransformation of tesevatinib in humans through drug-drug interactions. There is also a moderate potential to inhibit CYP2C8, CYP2D6 and CYP1A2 although this is most likely to occur at higher concentrations than those expected in this study.

Due to these interactions and potential interactions, inhibitors and inducers of CYP3A4, CYP2C8, CYP2D6, and CYP1A2 should be avoided if a substitute is available or otherwise used with caution in all patients while receiving study drug. In addition, patients must be closely monitored for the desired drug effect and potential AE.

Substrates of isoenzymes CYP3A4, CYP2C8, CPY2D6 and CYP1A2 may be used with appropriate clinical monitoring.

See Appendix 4 for a list of drugs that are clinically relevant inhibitors and inducers of CYP3A4, CYP2C8, CYP2D6, and CYP1A2.

# 9.3.3.1. Management of Patients Requiring Concomitant Medications Associated with QT Interval Prolongation

Tesevatinib has been associated with prolongation of the QT interval. Patients requiring treatment with drugs known to be associated with torsades de pointes or significant QT interval prolongation may not be enrolled into this study (see Appendix 4).

Drugs associated with QT interval prolongation should be avoided in patients receiving study drug unless deemed clinically necessary. Should a patient develop a condition for which a medication known to affect QT interval is indicated, consideration should be given to the

additive risk of QT interval prolongation versus the potential benefit of treatment with the required medication and/or study drug. Contact the Medical Monitor prior to the administration of the concomitant medication.

As of Amendment 4 this will not be applicable—During long-term follow-up, patients who require short-term (2 to 3 weeks, not to exceed 21 days) treatment with a concomitant medication associated with QT interval prolongation while receiving study drug should have the study drug held until the concomitant treatment course is complete. The decision about whether the patient can continue on trial following this interruption will be determined by the Medical Monitor.

During long-term follow-up, patients who require chronic treatment with a concomitant medication associated with QT interval prolongation while receiving study drug should be monitored as follows:

- Three ECGs should be obtained prior to start of the concomitant medication. These ECGs should be obtained within a total span of 30 minutes with an interval of approximately 1–2 minutes between recordings.
- If the average QTc interval from these 3 ECGs is > 60 msec above the average baseline (Day 1 predose) value or is ≥ 500 msec, study drug may be discontinued or dose reduced after discussion with the Medical Monitor.
- If both of the above criteria are not met (i.e., the average QTc interval is no more than 60 msec above baseline and is < 500 msec), ECGs should be obtained daily for the first 3 days of treatment with the concomitant medication.
- Additionally, an ECG should be obtained weekly for 2 weeks, then every 2 weeks for 1 month and monthly thereafter until the concomitant medication is no longer required or study drug is discontinued.

QTc interval prolongation should be managed as noted in Section 9.1.4.3.

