MRI will be used to evaluate the tumor at baseline (within 7 days of study drug administration). All MRIs taken on study patients will be submitted to the sponsor for possible retrospective analysis (refer to Section 10.1).
Subjects who have completed 24 cycles of treatment and who continue to tolerate treatment with KD019 may continue on study with bimonthly visits to clinic for drug dispensing, safety and efficacy assessment.

	End of Treatment Visit		
	An End-of-Treatment visit is to be performed as soon as possible after the patient's last dose of study drug. This may occur at the visit at which disease progression is diagnosed. The patient will continue to be followed in the study for disease progression and survival.		
	Follow-Up Period		
	A follow-up visit will occur 30 days (±5 days) after the last dose of study drug. Patients will undergo PEs; vital sign measurements; hematology, serum chemistry, urinalysis and ECG, all performed prior to the start of any new therapy. This visit may occur prior to 30 days if a new therapy is started within 30 days of last dose of study drug. If progressive disease has not occurred at the end of the follow-up period MRIs should be repeated every 8 weeks until disease progression per RANO criteria.		
	Long-Term Follow-Up		
	Patients are to be contacted by telephone every 8 weeks to assess progression status if not PD when study drug stopped, survival status and any subsequent anti-cancer treatment. If PD was not observed before the 30-day follow-up period, patients will return for follow-up MRI until PD is demonstrated or they start a new anti-cancer treatment.		
	As of Amendment 4, long-term follow-up will no longer be required.		
Study population/Number of patients	A total of approximately 40 patients with recurrent glioblastoma will be enrolled at up to 10 US centers.		
Diagnosis and main	Inclusion criteria:		
criteria for inclusion	Patients will be included if they meet the following criteria:		
	1) Willingness and ability to provide written informed consent and to comply with the study protocol as judged by the investigator		
	2) Age $\geq$ 18 years old		
	3) Karnofsky performance status (KPS) ≥70% (see Appendix 1).		
	4) Stable or decreasing dose of corticosteroids within 5 days prior to study enrollment.		

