First appearance	
 
No action with study drug
 
For diarrhea start loperamide, monitor for dehydration
 
For rash start topical steroids (see Section 9.1.4.2)
 
For QTc prolongation no action
 
	
 
No action with study drug
 
For diarrhea start/increase loperamide, monitor for dehydration
 
For rash topical steroids ± doxycycline (see Section 9.1.4.2)
 
For QTc check con-meds and electrolytes, correct as indicated
 
For confirmed pneumonitis interrupt and consult Medical Monitor
 
	
 
Interrupt treatment until resolved to Grade 0-1. If interruption < 21 days restart at 250 mg/day. If interruption ≥ 21 days, check with Medical Monitor.
 
In addition, for QTc check con- meds, electrolytes and consult Medical Monitor (see Section 9.1.4.3.1 for restarting and monitoring instructions).
 
For creatinine in absence of renal dysfunction no interruption.
 
	Discontinue. Consult Medical Monitor if continuation is in patient's best interest. In addition, for QTc hospitalize patient and perform cardiology evaluation (see Section 9.1.4.3.1)
appearance			drug	drug

# 9.1.3.1. Requirements for Continuation of Treatment Post Cycle 1

Patients must fulfill the following criteria in order to commence a new cycle of treatment:

- all related  $\geq$  Grade 3 AEs have resolved to  $\leq$  Grade 1
- serum potassium and magnesium above the lower limit of normal
- no arrhythmias, pathologic bradycardia, or associated symptomology
- $QTcF \le 470$  msec and increase from baseline  $\le 60$  msec unless Medical Monitor has given permission to continue
- no concurrent medications that prolong QTc (see Appendix 4)
- no evidence of progressive disease
- no additional therapeutic interventions for glioblastoma
- no strong inhibitors or inducers of CYP3A4, CYP2C8, CYP2D6 or CYP1A2 (see Appendix 4)

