### 9.1.4.3. QT Interval Prolongation

Patients should be carefully monitored for symptoms of arrhythmia (i.e., dyspnea, chest pain or tightness, palpitations, dizziness) and for episodes of syncope. An ECG should be obtained if these symptoms occur. In addition, serum potassium and magnesium must be maintained within the normal range and may require additional monitoring or adjustment if patients develop diarrhea. Medications with potential for QTc(F) prolongation should not be used concurrently or started within 24 hours of tesevatinib administration (see Appendix 4).

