# 9.3. Concomitant Medication and Treatment

If the patient must use a concomitant medication during the study, it is the responsibility of the principal investigator to ensure that details regarding the medication are recorded on the eCRF.

Patients should avoid ingesting grapefruit, pomelo or Seville orange fruits (and juice) with tesevatinib or at any time during the study. Patients should not take medications that are associated with a risk of QTc interval prolongation and/or torsades de pointes. Additionally, patients are not permitted to take concomitant medications that strongly inhibit (e.g., ketoconazole, itraconazole, erythromycin, clarithromycin) or induce (e.g., phenytoin, carbamazepine, rifampicin, or phenobarbital) the CYP3A4 isozyme. Steroid medications are allowed.

Administration of acid-reducing medications should be avoided during the study as these agents may decrease exposure to tesevatinib. If acid-reducing agents are needed, H-2 antagonists or antacids will be recommended rather than proton pump inhibitors. Administration of acid-reducing agents such as H-2 antagonists or antacids, if required, should take place no less than 2 hours before or after dosing with tesevatinib.

Since tesevatinib is a potent inhibitor of MATE transporter proteins, increased levels of concomitant medications that are secreted by the kidney proximal tubule cells into the renal tubule by MATE transporter proteins may occur. Thus subjects taking cephalexin, cimetidine, dofetilide, fexofenadine, metformin, procainamide, and pyrimethamine should be monitored carefully (see Appendix 4).

Other prohibited treatments include the following:

- Other investigational drugs
- Concurrent anti-tumor therapies such as chemotherapy, gene therapy, biologics, radiation therapy, or other immunotherapy
- Warfarin or other anti-coagulant drugs (Low dose low molecular weight heparin given for deep vein thrombosis (DVT) prophylaxis is allowed)
- Medications known to moderately or severely inhibit the CYP3A4 isozyme or any drugs that are moderate or severe CYP3A4 inducers. A stable regimen (≥ 4 weeks) of antidepressants of the SSRI class is allowed (common SSRIs include escitalopram oxalate, citalopram, fluvoxamine, paroxetine, sertraline, and fluoxetine)

• Drugs associated with torsades de pointes or known to prolong the QTc interval, including anti-arrhythmic medications within 2 weeks prior to Day 1 of treatment on study

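### QTc-prolonging co-medication is barred in Sections 9.1.3.1, 9.1.4.3 and 9.3 but allowed by exception in 9.3.3.1, whose own hold and ECG rules cover no patient as written

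*Protocol*

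**What the plan says.** Three parts of the protocol's treatment rules bar QTc-prolonging co-medication:

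- Section 9.3: "Patients should not take medications that are associated with a risk of QTc interval prolongation and/or torsades de pointes".
- Section 9.1.4.3: "Medications with potential for QTc(F) prolongation should not be used concurrently or started within 24 hours of tesevatinib administration".
- Section 9.1.3.1, among the criteria a patient must meet before each new cycle: "no concurrent medications that prolong QTc".

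Exclusion criterion 16 and the synopsis list of prohibited treatments point the same way. The synopsis item runs on to mention the 2 weeks before Day 1, so it could be read as an entry rule only.

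Section 9.3.3.1 is permissive: "Drugs associated with QT interval prolongation should be avoided in patients receiving study drug unless deemed clinically necessary". It asks for the added QT risk to be weighed against benefit and for contact with the Medical Monitor before the drug is given. Two specific rules follow. For short courses (up to 21 days), study drug is held until the course ends. For chronic use, there is an ECG schedule, introduced as applying to "During long-term follow-up, patients who require chronic treatment with a concomitant medication associated with QT interval prolongation while receiving study drug". The hold paragraph carries the same two conditions and is preceded by a statement that it does not apply as of Amendment 4.

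The synopsis describes long-term follow-up as telephone contact every 8 weeks to "assess progression status if not PD when study drug stopped, survival status and any subsequent anti-cancer treatment", and says that it is no longer required as of Amendment 4.

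**The concern.** There are two linked problems. First, a site cannot tell from the text whether a patient on study drug may receive a QTc-prolonging medicine: 9.3.3.1 gives a route, and 9.1.3.1 then blocks the next cycle for a patient who has taken it and is still on the medicine. Second, the precautions written for that route are attached to a period in which nobody takes study drug.

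At stake is consistent safety handling between sites, for a drug whose QTc effect the protocol describes as rising with plasma concentration, in a study with no Data Monitoring Committee (Section 11.5). There is also a smaller reporting consequence. If sites fill the gap with unscheduled ECGs, SAP Section 3.10 places those results in listings and leaves them out of the summary tables.

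**Working it through.** The protocol states no figure for this point, so the check sets passages side by side and places the study periods in time.

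**1. Do the bars and the permission conflict?** Sections 9.3 and 9.1.4.3 could be read as general rules to which 9.3.3.1 is the exception. Section 9.1.3.1 is harder to read that way. Its QTcF criterion carries an express waiver if the Medical Monitor permits continuation. The co-medication criterion in the same list carries none. A patient who uses the 9.3.3.1 route and is still on the medicine at the next Day 1 therefore fails a criterion for starting the cycle, even if the Medical Monitor was consulted.

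**2. When is long-term follow-up?**
- The 30-day visit is held 30 days (±5) after the last dose (Table 1 footnotes; Section 12.2.13).
- Telephone contact begins 8 weeks after that visit (Section 12.2.14).
- The nominal first contact after the last dose is 30 + 56 = 86 days, with a range of 25 + 56 = 81 to 35 + 56 = 91 days.
- The 30-day visit may be brought forward if new therapy starts, but it still follows the last dose.
- In Table 1, the long-term follow-up column shows MRI and telephone contact, with no tesevatinib dosing and no ECG.

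**3. Can a patient meet both conditions?** The hold and ECG rules each require the patient to be in long-term follow-up and to be receiving study drug. From step 2, these periods do not overlap. The bimonthly visits after Cycle 24 are on drug, but the protocol nowhere calls them long-term follow-up. Since Amendment 4 the period itself is no longer required. As written, the two rules cover no patient.

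**4. What does the Amendment 4 marker cover?** It stands immediately before the hold paragraph. The ECG paragraph follows as a separate paragraph without a marker. The text does not say whether the marker extends to it. Under either reading, step 3 leaves both rules without effect.

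**5. What scheduled ECGs remain?**

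| Period | Scheduled ECGs | Longest nominal gap |
|---|---|---|
| Cycle 1 | Day 1 and Day 15, then Cycle 2 Day 1 | 14 days |
| Cycles 2 to 24 | Day 1 of each 28-day cycle | 28 days |
| After Cycle 24 | every second cycle | 2 × 28 = 56 days |

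Visit windows of ±3 days make these approximate. For comparison, the schedule in 9.3.3.1 that cannot operate calls for three ECGs before the medicine is started and then, if the stated QTc limits are not exceeded, daily ECGs for 3 days. It also calls for weekly ECGs for 2 weeks and less frequent ones after that.

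**The case against.** The best reply is that this is a general bar with a specific exception, and that the two are linked. Sections 9.1.3.1 and 9.1.4.3 both refer to Appendix 4, and Appendix 4 says that QTc-risk drugs are to be avoided as set out in 9.3.3.1. That link is real, so the sections are not wholly unconnected. It does not settle step 1 above: the new-cycle criterion still has no exception, and Appendix 4 adds none.

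The second reply is that general safeguards remain, and this stands. They are Medical Monitor contact before the medicine is given, routine Day 1 ECGs, an ECG if arrhythmia symptoms or syncope occur, maintenance of potassium and magnesium, unscheduled ECGs, and management of any prolongation under 9.1.4.3. Section 11.5 also promises attention to such co-medication. A reader might infer that patients using the exception go unmonitored; the documents do not support that. What is missing is a hold rule and ECG schedule specific to the co-medication.

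Three other stronger readings also fail:

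- **That 9.1.3.1 obliges the patient to stop treatment.** It sets conditions for commencing a new cycle and does not order discontinuation.
- **That the roughly 20% QTc prolongation in Section 5.2 measures the size of this gap.** It is a background rate from machine-read ECGs, mostly in lung cancer patients, with no Grade 4 events and no associated clinical findings. It says nothing about co-medication.
- **That the 56-day gap is typical.** It applies only after 24 cycles, 24 × 28 = 672 days or about 22 months, against an assumed median PFS of 4.5 months.

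**Conclusion.** The inconsistency holds on the text. Three sections bar QTc-prolonging co-medication during treatment, one allows it, and the new-cycle criterion in 9.1.3.1 cannot be met while the permitted medicine continues. The hold rule and ECG schedule in 9.3.3.1 apply to nobody, because long-term follow-up begins only after the last dose and is no longer required. The reach of the Amendment 4 marker is unclear.

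The consequence is limited. A patient using the exception keeps the general safeguards but has no operative rule specific to the co-medication, and may wait up to about 28 days for the next scheduled ECG, or about 56 days after Cycle 24. These gaps are worst cases that assume no symptom-triggered or unscheduled ECG. The documents do not say how many patients would use the exception; the number is probably small. A reader might also infer an effect on PFS-6 or on the QTcF summaries, but nothing in the documents shows one. The point matters for patient safety and consistent conduct, and it is cheap to settle.

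**What to change.** Reconcile Sections 9.1.3.1, 9.1.4.3, 9.3 and 9.3.3.1, Appendix 4 and the synopsis so that one consistent rule governs QTc-prolonging co-medication during study treatment. If an exception is kept, the new-cycle criterion in 9.1.3.1 needs to agree with it. State which paragraphs of 9.3.3.1 the Amendment 4 marker covers. The sponsor and its safety experts should then name the study period to which any retained hold or ECG rule applies, so that it can operate. Whether to keep the exception, the hold or the ECG schedule is a clinical decision for the sponsor, and this point takes no position on it.

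The cost is a protocol clarification and a letter to sites. If an ECG rule is retained, it would add at most some ECGs in the few patients concerned.

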# 10. EFFICACY ASSESSMENTS

Disease assessments will be based on the RANO criteria [Wen 2010] and will comprise radiological assessments (MRI), clinical assessments (KPS), and corticosteroid use. Based on radiological assessments, clinical status, and corticosteroid use, an overall evaluation of CR, PR, SD, or PD should be made at each disease assessment after baseline according to the RANO criteria (Appendix 2).

Disease assessment during the screening period is to be performed within 7 days before study drug administration and must be used as the baseline radiological assessment. Per the study's schedule of assessments (see Table 1), disease assessment is intended to be done prior to starting cycle 2, 3, 5, 7+. The corticosteroid dose should be kept stable for 5 days prior to the MRI scan. During the study, disease assessments should be performed at week 4 and week 8 after the date of first study treatment and then every 8 weeks (at Week 16, 24, etc.), regardless of treatment delays. For patients who discontinue treatment for other reasons than PD, disease assessment in the follow-up period should continue every 8 weeks (according to the original schedule) until disease progression. For patients with PD, disease assessment at the EOS is only required if not performed within the previous 8 weeks.

Disease assessments as initially planned according to the schedule of assessments should be maintained regardless of treatment delays. Unscheduled disease assessments may be performed at the discretion of the investigator to allow a decision on further study treatment administration for individual patients. For patients who discontinue treatment for reasons other than progressive disease, disease assessment in the follow-up period should continue every 8 weeks (according to the original schedule) until disease progression.

# 10.1. Radiological Assessment by Brain MRI

The acquisition protocol for MRI (provided as a separate document) will provide further details for scan standardization. All efforts should be made to perform MRI scans according to the corresponding specification in order to ensure that quality of MRI will be standardized among all sites. Consistency of subsequent MRIs should be ensured during all assessments for each patient, with the same technique being used for evaluating lesions. Patients should be imaged on the same MRI scanner for the duration of the study. A 1.5T or 3T scanner must be used for this study. The use of IV contrast should, as long as clinically possible, be kept consistent.

The following sequences of the entire brain must be acquired:

- T1 pre-gadolinium
- T2/FLAIR
- T1 post-gadolinium

Target Lesions: Lesions should be measured on the greatest size (bi-dimensional measurement of the longest cross-sectional diameters) observed either on axial, coronal, or sagittal slices, and the most representative observed chosen to be followed for response evaluation (i.e., once selected at baseline, the plane should be maintained across the study, to allow comparison). If there are

multiple contrast- enhancing lesions, a minimum of two of the largest lesions, and a maximum of five lesions, should be measured, and the sum of the products of the perpendicular diameters of these lesions should be determined. Occasionally, the largest lesions may not lend themselves to reproducible measurements, and the next largest lesions that can be measured reproducibly should be selected. For patients with recurrent disease who have multiple lesions of which only one or two are increasing in size, the enlarging lesions should be considered the target lesions for evaluation of response.

Nontarget Lesions: All other lesions will be considered nontarget lesions and should also be recorded. Rarely, unequivocal progression of a nontarget lesion requiring discontinuation of therapy or development of a new contrast-enhancing lesion may occur, even in the setting of stable disease or partial response in the target lesions. These changes would qualify as progression.

Tumor measurements should be made by the same investigator/radiologist for each patient during the study to the extent that this is feasible.

A radiological assessment of complete response (CR) or partial response (PR) requires confirmatory imaging at least 4 weeks after the initial assessment of response was observed. In the event that the radiographic changes are equivocal and it is unclear whether the patient has stable or progressive disease, treatment should be continued and the patient should be closely observed. If subsequent imaging studies demonstrate that progression has occurred, the date of progression should be the date of the scan at which disease progression was first suspected.

Sites should save all MRI images as DICOM files or other standard format with unique descriptive file names (e.g. study number, patient initials and number, date and image sequence number) on to anonymized DVD(s) and provide these to the Sponsor upon request.

